The major difficulty in evaluating BA is preventing the control group from cross-contamination (7). In the implementation process of BA, according to the BASRCT manual, all physicians, all inpatient and outpatient staff as well as managers need to be informed and undergo basic education regarding the intervention (4). As BA addresses a prevalent and frustrating issue in psychiatric health care, there is considerable risk that the approach leaks to the control group, reducing the possibility to detect between-group differences. For example, staff have shared experiences of a change in the workplace alongside their work with BASRCT, related to a development of more positive attitudes towards all patients at the inpatient unit (11). Indeed, in BASRCT both the BA and control group demonstrated a significant within-group decrease in general psychiatric admissions.

In this project we aim to address these methodological difficulties in exploring the effects of BA, by making use of the richness of existing data in the Swedish regional and national registers (7). We will evaluate effects of implementing BA within sites, comparing data from before and after implementation. We will also compare equivalent sites which have implemented BA at different timepoints, using relevant clinical data from registers.

PROJECT DESCRIPTION

METHODS

Research questions will be evaluated through registers, i.e. no new data will be collected from individual participants. A cohort will be created including all individuals fulfilling inclusion criteria. There are two cities where the standardized version of BA is fully implemented, with a separate ward for BA (Lund and Helsingborg). Two equivalent cities of similar size and distribution, implementing the same standardized version at a later timepoint, were found (Linköping and Norrköping). In Lund, BA was implemented in 2015, as compared to 2021 in Linköping. In Helsingborg, BA was implemented in 2017, compared to 2021 in Norrköping. Retrospective data from 2010-2022 as well as prospective data, from the date of inclusion until 2025-12-31, death or moving out of the uptake area, will be used.

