National Patient Register

- Data on compulsory care (admissions and compulsory acts), Diagnoses, Age, Gender
- Motivation: primary and secondary outcome measures

National Cause of Death Register

- Cause of death
- Motivation: secondary outcome measure

The Total Population Register

- Gender, Marital status, Country of birth, Spouse or registered partner, Cohabitation, Date of death.
- Motivation: To secure that included individuals live in the uptake areas and to adjust for potential confounding factors/effect modifiers.

National Prescribed Drug Register

- Drugs retrieved from the pharmacy: Number of packages, Anatomical Therapeutic Chemical code (ATC-code), date of expiry, corresponding daily dose
- Motivation: Certain medical conditions are well captured by prescribed drugs. This is informative with regard to confounding factors/effect modifiers.

Longitudinal Integrated Database for Health Insurance and Labour Market Studies

- Income, means of subsistence, number of persons in the household
- Motivation: Obtaining information on confounding factors/ effect modifiers that we need to adjust for alternatively make separate subgroup analyses.

STATISTICAL ANALYSES PLAN

The following comparisons will be performed:

BRIEF ADMISSION BY SELF-REFERRAL FOR INDIVIDUALS WITH SELF-HARM.

Effects on compulsory care.

- Within sites, before and after introduction of BA.
- Pairwise, between equivalent sites, before BA was introduced.
- Pairwise, between equivalent sites, after BA was introduced at one of them.
- Pairwise, between equivalent sites, after BA was introduced at both.
- Between men and women, adjusted for age and diagnoses.

Overall, the studies will have good statistical power, which can be illustrated with the following example. If we assume that about 50% of the individuals receiving treatment as usual had at least one admission that was >7 days, and with 80% statistical power we want to find a significant decrease (i.e. $p<0.05$) to 25% when BA was introduced, then 66 individuals have to be included in each group. In Lund about 40 patients are recruited each year, which means that we will have at least 200 patients in each group in a five-year period. Preliminary data indicates that halving the number of days with compulsory admission is a reasonable assumption, and in addition it is also of clinical significance.

SIGNIFICANCE

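### Each early site is compared with one late site although both late sites lack BA until 2021; adding the second would make each early-site estimate modestly more precise and less dependent on one comparator

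*Combined protocol and SAP*

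**What the plan says.** The Statistical analyses plan lists three between-site comparisons, all pairwise: before BA, after BA at one site, and after BA at both. The middle one carries the exposed-versus-unexposed contrast: "Pairwise, between equivalent sites, after BA was introduced at one of them". The list itself does not name the pairs.

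The Methods section does so by implication. It introduces the late cities together: "Two equivalent cities of similar size and distribution, implementing the same standardized version at a later timepoint, were found (Linköping and Norrköping". It then sets the dates side by side: "In Lund, BA was implemented in 2015, as compared to 2021 in Linköping" and "In Helsingborg, BA was implemented in 2017, compared to 2021 in Norrköping". The data window is "Retrospective data from 2010-2022 as well as prospective data, from the date of inclusion until 2025-12-31". All four uptake areas are in the inclusion criteria.

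No pooled, four-site or cross-pair analysis is listed. The Significance section gives the later-implementing sites the job of allowing correction for other trends in care.

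**The concern.** Linköping and Norrköping are both without BA from 2015 through 2020. That span covers the whole period in which Lund is exposed and they are not, and likewise 2017 through 2020 for Helsingborg. The second comparator costs no new data. The Methods section describes the two late cities jointly and gives no criterion that ties one of them to one early city only.

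Two things are at stake for each early site's own result. Its interval is wider than the collected data allow. More importantly, a local change at the single late site, for instance in bed numbers or diagnostic practice, cannot be told apart from a BA effect in that pair, and no listed analysis would show whether the result depends on the choice of comparator. In 2015 and 2016, when only Lund is exposed, Norrköping's unexposed data play no part in the Lund contrast.

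**Working it through.** **Inputs from the documents.** BA starts: Lund 2015, Helsingborg 2017, Linköping and Norrköping 2021 (Methods). Power example (Statistical analyses plan): "about 50% of the individuals receiving treatment as usual had at least one admission that was >7 days"; "we want to find a significant decrease (i.e. $p<0.05$) to 25% when BA was introduced"; "with 80% statistical power"; 66 per group needed; about 40 patients a year in Lund, hence at least 200 per group over five years.

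**Assumptions.** Equal site sizes, 200 at every site (40 × 5, a Lund figure), and independent sites unless stated. The documents give no variance for days per year and no between-site variance or correlation.

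**1. The plan's own figure.** For 50% v 25%, two-sided 5%, 80% power, the usual two-proportion formula gives 58 per group, and 66 with continuity correction. The stated 66 reproduces.

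**2. One comparator or two.** With one unit of variance per site:
- one late site: 1 + 1 = 2
- two late sites: 1 + 1/2 = 1.5
- variance ratio 1.5/2 = 0.75; SE ratio √0.75 = 0.866, so the SE is 13.4% lower

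The same ratio holds for change from baseline if the before and after periods scale alike. A change at one late site has weight 1 in a pair and 1/2 in the two-site contrast.

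**3. Shared regional changes.** With correlation ρ between the late sites, the site-level SE ratio is √[(1 + (1 + ρ)/2)/2]: 0.90 at ρ = 0.25, 0.94 at 0.5, 0.97 at 0.75 and 1.00 at 1.

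**4. The plan's binary example at 200 per site.**
- One late site: √(0.25/200 + 0.1875/200) = 0.0468, 95% half-width 9.2 points, power 99.95%
- Two late sites: √(0.25/400 + 0.1875/200) = 0.0395, half-width 7.7 points, power above 99.99%
- At an assumed smaller effect, 50% v 37.5%: power 71% to 83%

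**5. The primary outcome, days per year.** Take SE(log ratio) = CV × √(1/n₁ + 1/n₂), where CV is the assumed SD/mean across individuals, and power = Φ(ln 2/SE − 1.96) for a halving. With after-period variance only:

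| Assumed CV | 200 v 200 | 200 v 400 |
|---|---|---|
| 2 | 93% | 98% |
| 3 | 64% | 76% |
| 4 | 41% | 52% |

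A change-from-baseline analysis also carries before-period variance. With equal, independent before-groups the variance doubles, and at CV 3 power is about 37% and 47%. The table shows the size of the gain; it does not predict the power of the added analysis.

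**6. The overall average.** The two planned pairs share no site, so over common years their average has variance (2 + 2)/4 = 1. With shared controls, each estimate has variance 1.5 and their covariance is 0.5, so the average has variance (1.5 + 1.5 + 2 × 0.5)/4 = 1. There is no gain.

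**The case against.** The strongest case against has four parts.

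- **Matching.** The listed comparisons are of levels within a period, and for levels the similarity of size and distribution matters. The Methods section also reports different diagnostic traditions between sites, a reason for caution in pooling. This stands as a reason to keep the pairs. It does not weigh against an added analysis of change from each site's own before period, where similar trends matter more than similar size.
- **Wording.** The plan does not name the pairs, so all pairs could be meant. The side-by-side dates in the Methods section suggest otherwise; if all pairs are intended, the plan should say so.
- **The research question.** The primary question asks about implementing BA, not about each site, and the average does not gain (step 6). That is correct. However, the plan specifies no average; it lists pairwise results.
- **Independence.** The planned pairs are two separate replications. With shared controls, a change at one late site affects both early-site results at half weight instead of one at full weight. This is a real cost.

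A reader might also infer that a second late site answers the bed reductions mentioned under Preliminary and previous results. It does not: those are offered as a possible explanation for the fall at Lund, and a change at the early site enters its estimate in full however many late sites are used.

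**Conclusion.** The point holds as a modest improvement in precision and robustness for each early site's own estimate. The SE falls by about 13% with equal-sized, independent sites, and by less at site level if the late cities share regional changes. A change at one late site drops from full to half weight. Robustness is the stronger reason.

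A reader might go further and infer that the plan discards half of its unexposed data, or that the study lacks power because of the pairing. The documents support neither. All four sites contribute to the listed comparisons, and the second late site is absent only from each early site's own contrast. On the plan's binary example, power is already 99.95% with one comparator. For days per year, power depends on a CV that the documents do not give. Keeping matched pairs is defensible and is not an error.

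**What to change.** Keep the planned pairs. Add to the Statistical analyses plan, before results are seen, one analysis that compares each early site's change from its own before period with the change at both late sites together, through the end of 2020. Report the cross pairs (Lund–Norrköping and Helsingborg–Linköping) as sensitivity analyses. Name the pairs explicitly, and state that the two added early-site estimates share controls and are not independent.

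The cost is some extra analysis of data already to be extracted, with no new participants. There are two downsides: the lost independence, and the use for each early site of a late site that was chosen to match the other. The retained pairs address both.
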